9.3 Analysis of Secondary Endpoints

Secondary endpoints will include post-treatment surgical resectability, and local control. Patients who are able to undergo surgical resection will be documented as having a microscopically complete (R0), microscopically incomplete (R1), or gross incomplete (R2) resection.

All patients included in the study will be assessed for response to treatment. Patients who do not demonstrate any local progression (patients with CR+PR+SD) at the primary site (using RECIST criteria by CT or MRI) will be considered to be locally controlled. Duration of local control (TLC) will be defined to be the time from the start of RT until clinical or RECIST progression, death from treatment toxicity, or last patient follow-up. Patients who experience clinical or RECIST progression, or death from treatment toxicity will be considered to have experienced a local control event; otherwise patients will be considered censored at last contact. The probability of LC as a function of time since RT will be quantified by the method of Kaplan and Meier (Kalbfleisch, 2002). The relative hazard for LC event according to assigned RT level will be calculated using the relative risk regression model of Cox, but formal statistical conclusions will not be drawn from this analysis.

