From a practical standpoint, if there existed an effective and safe means to achieve local control and contract the length of RT into two weeks, patients would be more likely to tolerate aggressive systemic therapy. Meanwhile, with a positive initial experience in the unresectable setting, SBRT could be studied in the preoperative setting (e.g., for resectable or borderline resectable patients).

Primary Objective: To assess the maximum tolerated dose of delivering three fractions of SBRT and identify the appropriate dose for unresected carcinoma of the pancreas or ampulla

Secondary Objectives: To define toxicities, the post-treatment pain score, and quality of life, the rate of post-treatment resectability, and local control (as measured by CT or MRI and defined as lack of progressive disease by RECIST criteria).

Study Design:

- Dose escalation schema: Patients will be enrolled in a 3+3 dose escalation schema including doses of 10 Gy, 12.5 Gy, and 15 Gy. Once the MTD is reached, patients will be treated in an expanded cohort.
- Radiation therapy: The primary tumor will be treated with stereotactic body radiation therapy in three fractions over 10 days. Fiducial markers will be placed prior to therapy, when possible, to assist with localization. Respiratory gating will be used to help address movement of the target due to respiratory motion. Constraints to surrounding critical structures (duodenum, liver, kidneys, and spinal cord) will be observed.
- Chemotherapy: No concurrent chemotherapy will be administered with the RT. Patients will be allowed to receive chemotherapy prior to RT, although this is not required. Post-RT chemotherapy will be at the discretion of the treating physicians.
- Surgery: ability to achieve resection will be documented by completeness of resection (complete microscopic, incomplete microscopic, or gross residual). Re-evaluation for resectability will be at the discretion of the treating physician and not be a requirement of the study.

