8. MEASUREMENT OF EFFECT

Although response is not the primary endpoint of this trial, patients with measurable disease will be assessed by standard criteria. For the purposes of this study, patients should be re-evaluated with CT or MRI of the abdomen at 3-5 weeks after RT, and every 6 months for the first year.

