8.1.2 Disease Parameters

Measurable disease. Measurable lesions are defined as those that can be accurately measured in at least one dimension (longest diameter to be recorded) as ≥ 10 mm with CT or MRI. All tumor measurements must be recorded in millimeters (or decimal fractions of centimeters).

Non-measurable disease. All other lesions (or sites of disease), including small lesions (longest diameter <20 mm with conventional techniques or <10 mm using spiral CT scan), are considered non-measurable disease.

Target lesions. The primary lesion (with immediately adjacent lesions) that will be treated with RT should be identified as the **target lesion(s)** and recorded and measured at baseline. Target lesions should be selected on the basis of their size (lesions with the longest diameter) and their suitability for accurate repeated measurements (either by imaging techniques or clinically). A sum of the longest diameter (LD) for all target lesions will be calculated and reported as the baseline sum LD. The baseline sum LD will be used as reference by which to characterize the objective tumor response.

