8.1.3 Methods for Evaluation of Measurable Disease

All measurements should be taken and recorded in metric notation using a ruler or calipers. All baseline evaluations should be performed as closely as possible to the beginning of treatment and never more than 4 weeks before the beginning of the treatment.

The same method of assessment and the same technique should be used to characterize each identified and reported lesion at baseline and during follow-up.

CT and MRI These techniques should be performed with cuts of 5 mm or less in slice thickness contiguously.

8.1.4 **Response Criteria**

8.1.4.1 **Evaluation of Target Lesions**

Complete Response (CR): Disappearance of the primary target lesion(s)

Partial Response (PR): At least a 30% decrease in the sum of the longest diameter (LD) of target lesions, taking as reference the baseline sum LD

Progressive Disease (PD): At least a 20% increase in the sum of the LD of target lesions, taking as reference the smallest sum LD recorded since the treatment started or the appearance of one or more new lesions

Stable Disease (SD): Neither sufficient shrinkage to qualify for PR nor sufficient increase to qualify for PD, taking as reference the smallest sum LD since the treatment started

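### The local-control event in Section 9.3 names no site, so read literally the Kaplan-Meier and Cox analyses can count a new distant lesion as a local failure

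*Combined protocol and SAP*

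**What the plan says.** Section 9.3 gives two rules for one endpoint.

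- **Status.** Locally controlled patients are described as "Patients who do not demonstrate any local progression (patients with CR+PR+SD) at the primary site", judged by RECIST on CT or MRI.
- **Time to event.** Duration of local control (TLC) is the "time from the start of RT until clinical or RECIST progression, death from treatment toxicity, or last patient follow-up". The event is then defined: "Patients who experience clinical or RECIST progression, or death from treatment toxicity will be considered to have experienced a local control event". For everyone else, "otherwise patients will be considered censored at last contact". These sentences name no site and do not refer back to the status rule.

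The TLC event feeds the Kaplan-Meier curve and a Cox model by assigned dose level. Section 9.3 says that no formal conclusions will be drawn from the Cox analysis.

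Four other places bear on the reading:

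- Section 8.1.4.1 defines progressive disease as a 20% increase in the sum of target diameters over the "smallest sum LD recorded since the treatment started or the appearance of one or more new lesions". The new-lesion limb has no site limit.
- Section 8.1.2 on target lesions: "The primary lesion (with immediately adjacent lesions) that will be treated with RT should be identified as the" target lesion(s).
- Section 1.2 and the Schema describe "local control (as measured by CT or MRI and defined as lack of progressive disease by RECIST criteria", again without a site.
- Section 8 schedules "CT or MRI of the abdomen at 3-5 weeks after RT, and every 6 months for the first year".

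The documents do not define clinical progression.

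**The concern.** Local control should describe what happens at the irradiated site. An event that also takes in new lesions elsewhere is closer to progression in general. Two analysts working from the same data, one using the status rule and one using the event sentence, could draw different curves under the same label.

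The case is foreseeable. Section 2.1 notes that these cancers can progress both locally and at a distance. Section 3.1.1 admits patients with distant metastases. The follow-up scan covers the abdomen, so it can show liver or other lesions away from the primary.

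Section 9.1 says that the phase II part will measure efficacy. Of the two secondary endpoints listed in Section 9.3, resectability depends on a re-evaluation that the Schema leaves to the treating physician. That leaves local control as the efficacy measure planned for all patients.

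**Working it through.** The plan states no sample size, power or target rate for local control, so there is no figure to reproduce. The check is a reading of the text, followed by the arithmetic of the consequence.

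**1. One patient under each rule.** Take a patient with a stable irradiated primary and a new liver lesion on the abdominal scan.

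| Text | Result |
|---|---|
| 9.3 status rule, primary-site wording | Locally controlled |
| 9.3 status rule, parenthesis (CR+PR+SD) with 8.1.4.1 as written | Unclear: a new lesion makes the RECIST category PD |
| 9.3 event sentence with 8.1.4.1 | Local-control event |
| 1.2 and Schema with 8.1.4.1 | Not locally controlled |

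The target-lesion definition in Section 8.1.2 restricts which diameters are summed. It cannot restrict the new-lesion limb, because a new lesion is not a baseline target. Nor does it restrict clinical progression.

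**2. Primary never fails.** Inputs: 18 patients at the MTD and up to 24 in all (Section 9.2). With r patients at risk and no earlier event, one extra event lowers the Kaplan-Meier estimate by 1/r.

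- r = 18: 1/18 = 5.6 points
- r = 24: 1/24 = 4.2 points
- r = 12 (6 of 18 censored earlier): 1/12 = 8.3 points

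For scale, suppose 15/18 = 83.3% are controlled (exact 95% CI 58.6% to 96.4%). One such patient gives 14/18 = 77.8% and two give 13/18 = 72.2%. Both lie inside that interval.

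**3. Primary fails after distant progression.** The literal rule moves the event to an earlier date, when more patients are at risk. Example: of 18 patients, patient A has a distant lesion at month 2 and local failure at month 10; 11 others are censored in months 3 to 8; there is no other event.

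- Literal rule at month 12: 17/18 = 94.4%
- Site-specific rule: at risk at month 10 = 18 − 11 = 7, so 6/7 = 85.7%

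Between months 2 and 10 the literal curve is the lower one (94.4% against 100%). After month 10 it is the higher one.

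Now let two of the six other patients still at risk at month 10 also have a distant lesion at month 2, with the primary controlled throughout. The literal estimate becomes 15/18 = 83.3%, while the site-specific one stays at 85.7%. The net late difference can go either way.

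**4. Total size.** This needs a distant-progression rate, which the documents do not give. As an assumption only, let the 12-month distant risk D run from 10% to 70%, independent of local failure, and start from 84% local control at 1 year (a rate cited in Section 2.2). The literal curve then reads 0.84 × (1 − D):

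- D = 10%: 0.84 × 0.90 = 76%
- D = 30%: 0.84 × 0.70 = 59%
- D = 50%: 0.84 × 0.50 = 42%
- D = 70%: 0.84 × 0.30 = 25%

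The width of this range shows that the size cannot be fixed from the documents. It is not an estimate for this trial.

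**The case against.** The strongest reply is that context makes the event local. The sentence defines the duration of local control and a local-control event, and it comes just after a sentence that names the primary site. The PD rule sits under the evaluation of target lesions. Target lesions are the irradiated primary and its immediate neighbours, complete response is disappearance of the primary target, and there are no non-target or overall-response rules. This is largely a primary-site framework. A reader might infer that the protocol chose a non-local endpoint, but the documents do not support that; loose drafting is the likelier explanation. What survives is that no passage limits new lesions or clinical progression to the primary, so the rule as stated still misclassifies the patient in step 1.

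Two other stronger readings are tempting.

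- **That the literal rule can only lower reported local control.** Step 3 shows otherwise. Heavy censoring is plausible, since Section 2.1 expects many patients to survive less than a year and deaths not due to treatment toxicity are censored.
- **That a few misclassified patients would reverse the comparison with the 84%, 57% and roughly 50% rates in Section 2.2.** Those rates are at 1 year, at 6 months and at no stated time respectively. Their event definitions are not given, and the plan sets no threshold or formal comparison against them.

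It is also fair to say that the stakes are limited: the endpoint is secondary, and the Cox analysis is descriptive.

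**Conclusion.** The concern holds as a defect in the event definition. The status rule and the event rule in Section 9.3 do not match. Taken literally with Section 8.1.4.1, the event rule mixes distant with local failure in a curve labelled local control.

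The size is about 5.6 points per patient whose primary stays controlled, assuming all 18 are still at risk and no event has occurred; it is larger after censoring. Where local failure follows distant progression, the fault is in the timing, and the late estimate can be too high. The overall size and direction are not known.

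One or two such patients would fall within sampling error in a cohort of 18. The mismatch is still one of definition, and more patients would not remove it. No sample size, dose decision or stopping rule depends on it. It should be fixed, at moderate priority.

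**What to change.** In Section 9.3, with matching wording in Section 1.2 and the Schema, define the local-control event as the first of:

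1. RECIST progression of the irradiated target lesion(s);
2. a new or recurrent lesion at, or immediately adjacent to, the primary site;
3. clinical progression documented at the primary site, with that term defined;
4. death from treatment toxicity, as now written.

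Then state that:

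- new lesions elsewhere are not local-control events and are reported separately as distant progression;
- primary-site assessment continues after distant progression, within the 12-month follow-up of Section 4.6;
- clinical deterioration not attributable to the primary site is not an event in the main analysis, with a sensitivity analysis that counts it as one;
- the CR+PR+SD parenthesis in the status rule refers to this same local definition.

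The general PD definition in Section 8.1.4.1 can stay. Record the site of progression (primary or elsewhere) on the case report form, if it is not already there; the form is not among the documents.

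The cost is wording and at most one data field, with no added visits, scans or patients. There are two downsides. Some clinical deterioration will be hard to assign to a site, which is why the default and the sensitivity analysis are needed. Deaths without local failure stay censored as now written, which can overstate local control and should be noted when the results are reported.

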1.2. Secondary Objectives

Secondary objectives include defining toxicities, effect on pain score, and quality of life, the rate of post-treatment resectability, and local control (as measured by CT or MRI and defined as lack of progressive disease by RECIST criteria).

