4.7 Criteria for Removal from Study

Patients will be removed from study (but followed for potential of toxicity) when any of the criteria listed in Section 4.4 applies. The reason for study removal and the date the patient was removed must be documented in the Case Report Form.

5. Radiation Therapy Guidelines

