7. STUDY CALENDAR

Baseline evaluations (including pain score, performance status, and medications) are to be conducted within 21 days prior to start of protocol therapy. Scans must be done within 28 days prior to the start of therapy. In the event that the patient's condition is deteriorating, laboratory evaluations should be repeated within 48 hours prior to initiation of therapy.

	Pre-treatment	Week 1 of RT	Week 2 of RT	Post-treatment
Inclusion/exclusion	X			
Informed consent	X			
Pathology confirming cancer	X			
History and physical	X	X	X	X ^f
Vital signs	X	X	X	X ^f
Performance status and pain score	X	X	X	X ^f
Documentation of current medicines	X	X	X	X ^f
CT or MRI of abdomen ^a	X			X ^a
Hematology ^b	X	X	X	X ^f
Chemistry ^c	X	X	X	X ^f
β-HCG ^d	X			
Patient QOL Questionnaire	X			X ^f
Toxicity assessment ^e		X ^e	X ^e	X ^f

a = Imaging will be done within 28 days of RT start, and in follow up at 3-5 weeks after completion of RT.

Further abdominal imaging will be performed every 6 months for the first year after RT.

b = CBC with differential, platelet count

c = comprehensive metabolic profile (glucose, sodium, potassium, chloride, carbon dioxide, BUN, creatinine, calcium, total bilirubin, alkaline phosphatase, AST, ALT). CA19-9 will be measured at months 1, 6, 12 from the start of radiation therapy, then every 6 months indefinitely (off protocol).

d = for women of child bearing potential, serum beta-hCG

e = prior to each radiation treatment after the first fraction, and with all other post-treatment clinic visits

f = From the start of radiation therapy, visits will be q2 weeks for the first month; then at months 2, 4, 6, 9, and 12; then every 6 months indefinitely (off protocol).

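### Local control is defined by imaging but censored at last contact, so a missed scan in year 1 biases it upward unless progression is found clinically

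*Combined protocol and SAP*

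**What the plan says.** Section 1.2 lists among the secondary objectives "local control (as measured by CT or MRI and defined as lack of progressive disease by RECIST criteria". Section 9.3 treats patients as locally controlled if they have not shown local progression by RECIST on CT or MRI, and then defines the duration as "time from the start of RT until clinical or RECIST progression, death from treatment toxicity, or last patient follow-up". Progression, clinical or RECIST, and death from treatment toxicity are events; "otherwise patients will be considered censored at last contact". The curve is estimated by Kaplan-Meier.

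The Study Calendar (Section 7) sets the scans: one "in follow up at 3-5 weeks after completion of RT", after which "Further abdominal imaging will be performed every 6 months for the first year after RT". I read the second part as about months 6 and 12. Visits are every two weeks in the first month, "then at months 2, 4, 6, 9, and 12; then every 6 months indefinitely (off protocol"). Months 2, 4 and 9 therefore have a visit and no scheduled scan.

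Section 8.1.1 requires that disease has been re-evaluated, but only for a patient to be evaluable for objective response. I found no rule in Section 9.3 or elsewhere for missed scans in the local-control analysis, and no definition of clinical progression.

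**The concern.** Being in contact is not the same as being assessed. Take a patient scanned once at about month 1, not scanned at month 6, and last seen at month 9. Under Section 9.3 this patient is in the month-6 risk set as event-free, although the measurement that defines the endpoint was not made. Growth of 20% in the primary tumour without symptoms would meet RECIST progression and could pass unnoticed at a clinic visit. Each such patient enlarges the denominator and can add an event only through clinical progression.

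The situation is plausible in this population. Patients with metastatic disease, ECOG 2 or a life expectancy only just above 3 months are eligible (Section 3.1), and such patients may be too ill to be scanned yet still be seen.

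The estimate also matters. Section 2.2 motivates the trial by setting 57% local control at 6 months in one SBRT study against 84% at 1 year in another and roughly 50% with standard fractionation. Section 9.1 says the phase II part will measure efficacy. An error of several points would blur that comparison.

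**Working it through.** The plan states no expected value, target or precision for local control, so there is no figure to reproduce.

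**Inputs from the documents.** Local control of 57% at 6 months (Section 2.2, used here as a scenario); scans at about months 1, 6 and 12 and visits at the listed months (Section 7); 18 patients at the MTD (Section 9.2).

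**Assumptions not in the documents.** Progression at a constant hazard; everyone scanned at month 1; a share m not scanned after that but in contact to month 12, unrelated to tumour status; a share c of progressions in these patients found clinically. I use m = 10%, 25%, 40% and c = 0, 0.5, 1.

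**Step 1: what the month-1 scan finds.** Control at month 1 is 0.57^(1/6) = 0.911. The share progressing between months 1 and 6 is 0.911 - 0.570 = 0.341.

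**Step 2: estimate at 6 months with censoring at last contact.** Nobody is censored before month 6, so the Kaplan-Meier estimate is one minus the detected share:

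estimate = 0.57 + 0.341 × m × (1 - c)

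- c = 0: 0.604, 0.655, 0.706, or about 60%, 66%, 71%.
- c = 0.5: 0.587, 0.613, 0.638, or about 59%, 61%, 64%.
- c = 1: 0.57 throughout, with no bias.

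Simulated Kaplan-Meier curves under the same assumptions agree.

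**Step 3: at 12 months.** The same hazard gives true control of 0.57² = 0.325. With c = 0 the estimate is 0.325 + (0.911 - 0.325) × m, or 0.383 at m = 10% and 0.559 at m = 40%.

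**Step 4: a cohort of 18.** Suppose 4 patients are unscanned at month 6 and 6 of the other 14 have progressed. Censoring the 4 at their last scan gives 8/14 = 57%. Keeping them at risk gives 12/18 = 67%.

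**Step 5: does moving the censoring date suffice?** With imaging as the only source of events, censoring at the last scan returns 57%. If unconfirmed clinical progression remains an event while event-free patients go back to their last scan, unscanned patients stay in the risk set only if they later fail. At m = 25% the simulated 6-month estimate is then 55% with half clinical detection and 54% with full detection, below the true 57%. Events and censoring must rest on the same assessments.

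**Step 6: when leaving is informative.** If 20% leave scanning and progress at twice the hazard, with no clinical detection, simulated true 6-month control is 52%. Censoring at the last scan gives 56% and at last contact 62%. The bias shrinks but does not vanish.

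**The case against.** The strongest reply is that Section 9.3 describes a composite endpoint. Clinical progression is an event, so every visit can reveal one, and censoring at last contact is coherent for such an endpoint. This stands in part: with full clinical detection the bias is zero. It does not settle the matter, because clinical progression is undefined, the objective is stated in imaging terms, and symptomless growth is not found at a visit.

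The second reply is scale. The endpoint is secondary and has no test or target. With 18 patients the 95% half-width at 57% is about 1.96 × √(0.57 × 0.43/18) = 0.23. That is larger than the bias in any 6-month case above. But imprecision is shown by an interval, and a one-directional bias is not. The disclaimer of formal conclusions in Section 9.3 covers only the Cox comparison.

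Three stronger readings are tempting, and the documents do not support them.

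- A reader might infer that the curve must go flat after month 12 because visits continue without scans. Section 4.6 ends protocol follow-up at 12 months, and Section 7 labels later visits off protocol. The inference holds only if those visits count as last contact, which Section 9.3 does not say.
- A reader might take 1 - 0.43 × (1 - m) as the 6-month estimate, giving 61%, 68% and 74% at m = 10%, 25% and 40%. That treats every failure as first detectable at month 6 and ignores both the 3-5 week scan and clinical detection.
- A reader might infer from Section 4.7 ("Patients will be removed from study (but followed for potential of toxicity") that removed patients are no longer scanned. No passage says so, and Section 9.3 intends a response assessment in all patients.

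Contact that continues after a clear scan also does no harm at the scan dates until a scheduled scan is missed.

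**Conclusion.** The point holds for scans missed within the first year. Censoring at last contact does not match the imaging definition in Section 1.2 and biases local control upward to the extent that progression in unscanned patients is not found clinically. In the 57% scenario the 6-month inflation is about 3 to 14 points for 10% to 40% unscanned with no clinical detection (0.034 to 0.136), about half that with half detected, and nil with full detection.

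The direction follows from the censoring rule. The size rests on the assumed unscanned share, the clinical detection rate, a constant hazard and leaving unrelated to tumour status. In a better-control scenario the effect is smaller: with true control of 84% at 12 months and no clinical detection, simulation gives 86% at 10% unscanned and 90% at 40%. This is worth correcting before analysis, but it does not touch the primary objective. The censoring of deaths not due to treatment toxicity is a separate question.

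**What to change.** In Section 9.3, make the main local-control curve imaging-based, as in Section 1.2:

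- Censor event-free patients at the last CT or MRI without local progression, or at day 1 if never re-imaged.
- Count clinical progression as an event only when CT or MRI confirms it.
- If an event is first found after a missed scheduled scan, censor at the last scan before the gap. Apply the same cut when the scan after the gap is clear; otherwise patients with a gap stay at risk only if they have not failed.
- End the curve at the month-12 protocol scan.

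Report the present composite (clinical or RECIST progression, censored at last contact) as a sensitivity analysis, define clinical progression for it, and give the numbers unscanned at months 6 and 12.

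The cost is a few sentences in Section 9.3; no visit, scan or patient is added. Follow-up times become slightly shorter, intervals wider and the curve less favourable. Some bias remains if patients who stop scanning progress faster, and the counts of unscanned patients let a reader judge how much that could matter.

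### Local control does not say how resection after SBRT is handled: unprogressed resected patients stay controlled to last contact, so the curve reflects SBRT plus any surgery

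*Combined protocol and SAP*

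**What the plan says.** Section 9.3 names two efficacy outcomes side by side: "Secondary endpoints will include post-treatment surgical resectability, and local control".

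**Local control.** A patient is controlled if there is no local progression: "Patients who do not demonstrate any local progression (patients with CR+PR+SD) at the primary site". The clock runs from the start of RT "until clinical or RECIST progression, death from treatment toxicity, or last patient follow-up". Progression and toxic death are events; "otherwise patients will be considered censored at last contact". The curve is estimated by Kaplan-Meier. A Cox model by dose level is added, with the statement that no formal conclusions will be drawn from it.

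**Surgery.** What Section 9.3 asks for is the margin status: "Patients who are able to undergo surgical resection will be documented as having a microscopically complete (R0), microscopically incomplete (R1), or gross incomplete (R2) resection". The Schema (Study Design, Surgery) leaves the decision outside the protocol: "Re-evaluation for resectability will be at the discretion of the treating physician and not be a requirement of the study".

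**Response.** Section 8.1.4.1 defines complete response by the lesion no longer being present ("Complete Response (CR): Disappearance of the primary target lesion(s"). Progression is a 20% increase from the smallest sum recorded, or a new lesion.

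**Timing.** Abdominal imaging is at 3-5 weeks after RT and then every 6 months in the first year (Section 7, note a; Section 8). On-protocol follow-up is 12 months or until death (Section 4.6).

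**The concern.** Resection takes out the lesion whose growth defines the endpoint. If the patient then stays in the risk set with no change of status, the months after surgery are counted as months of local control after SBRT. The more patients the treating physicians send to surgery, the better the curve can look, whatever SBRT itself did to the tumour. Two secondary endpoints that should be read separately become mixed.

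This matters for interpretation. Section 9.1 says the phase II part will measure efficacy. Section 2.2 motivates the trial with conflicting local-control reports: 57% at 6 months in one three-fraction study, 84% at 1 year in a single-fraction series, and roughly 50% with standard fractionation. Readers will set this trial's curve against those figures, and the plan gives no label saying that the curve includes the effect of later surgery.

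**Working it through.** The plan gives no target, power or expected rate for local control, so there is no stated figure to reproduce. The check has two parts: what the rules do with a resected patient, and how large the effect could be.

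**Part 1: following a resected patient through the rules**

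1. At surgery the patient has not progressed, so no event has occurred. Resection is not in the list of events or of times that end the clock.
2. After surgery, no progression means no event. The patient is censored at last contact, not at surgery. This holds for any non-progression response category, so it does not depend on how response is scored.
3. Regrowth, a new lesion or clinical progression after surgery is still an event.
4. On response, the complete-response definition has no exception for a lesion removed by surgery, so a complete resection could be read as a complete response. No section says so in words. An R2 resection leaves gross disease and need not qualify.
5. No other section makes resection a reason for non-evaluability or the subject of a sensitivity analysis.

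**Part 2: size, for illustration**

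Inputs from the protocol:
- 18 patients at the MTD (Section 9.2).
- SBRT-only control of 57% at 6 months (low scenario) or 84% at 12 months (high scenario), both from Section 2.2.

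Assumptions, not in the documents:
- Exponential local-control curve, S(t) = exp(−λt).
- r = 2 or 4 of 18 patients resected, all at month 3, all event-free at that time.
- Resection unrelated to later progression risk.
- No local progression after resection. For that timing and number resected, this is an upper bound.

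As-written curve for t > 3: r/18 + (S(3) − r/18) × exp(−λ(t − 3)).

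A curve censored at resection estimates S(t). The difference is therefore

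gain = (r/18) × (1 − exp(−λ(t − 3))).

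*Low scenario.* exp(−3λ) = √0.57 = 0.755; exp(−9λ) = 0.57^1.5 = 0.430; S(12) = 0.57² = 0.325.
- 6 months: r = 2 gives 0.111 × 0.245 = 0.027; r = 4 gives 0.222 × 0.245 = 0.054.
- 12 months: r = 2 gives 0.111 × 0.570 = 0.063; r = 4 gives 0.222 × 0.570 = 0.127.

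*High scenario.* exp(−9λ) = 0.84^0.75 = 0.877.
- 12 months: r = 2 gives 0.111 × 0.123 = 0.014; r = 4 gives 0.222 × 0.123 = 0.027.

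| Scenario | Time | SBRT only | 2 of 18 resected | 4 of 18 resected |
|---|---|---|---|---|
| Low | 6 months | 57.0% | 59.7% | 62.4% |
| Low | 12 months | 32.5% | 38.8% | 45.1% |
| High | 12 months | 84.0% | 85.4% | 86.7% |

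*Sensitivity.*
- Surgery at month 4: the low-scenario gain at 6 months falls to 1.9 points (0.111 × (1 − 0.57^(1/3))) for r = 2 and 3.8 points for r = 4. Earlier surgery would raise it.
- Surgery only halves the hazard: the low-scenario gain at 12 months is 0.111 × (√0.430 − 0.430) = 0.025 for r = 2 and 0.050 for r = 4.
- Surgery has no effect on local progression: the gain is zero.
- Curve drawn on all 24 patients with the same number resected: every gain is multiplied by 18/24 = 0.75.

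**The case against.** **Following everyone regardless of later treatment is a coherent definition.** Chemotherapy after RT is also discretionary and is not a censoring reason, so why single out surgery? This stands in part. The as-written curve is a legitimate quantity if it is labelled as control under SBRT plus later care. Surgery differs in that it removes the assessed lesion itself and is a separate endpoint of the same section, so its contribution can be shown cheaply.

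**Censoring at surgery may be informative.** Section 2.2 calls resectability the leading prognostic factor. This stands, and it is why the censored curve should be a sensitivity analysis and not a replacement.

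**The number resected may be small.** Patients may be metastatic or have local recurrence after earlier surgery (Section 3.1), and the 40% resection figure in Section 2.2 concerns carefully selected borderline resectable patients. This stands: 2 and 4 of 18 are illustrative, with no source in the documents. The assumption of no later progression is also extreme, since Section 2.1 itself notes frequent recurrence of ampullary cancer after surgery.

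**Stronger readings that a reader might infer are not supported.**
- *That the plan explicitly scores a resected tumour as a complete response.* It does not. That is an inference from the word for disappearance. The section also adopts published RECIST criteria, whose treatment of surgical removal cannot be seen here.
- *That a resected patient is counted as controlled whatever happens next.* Progression after surgery is still an event.
- *That the gain is S × (18 − r)/18 + r/18.* This gives 62% and 67% at 6 months in the low scenario, but it treats resected patients as event-free from day 0. Those resected while controlled have already come through the first months, so the month-3 gain at 6 months (2.7 and 5.4 points) is a little over half of what that formula gives (4.8 and 9.6).

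**Conclusion.** The point holds as a cheap improvement. Section 9.3 as written keeps a resected, unprogressed patient in the risk set to last contact, and nothing else in the plan addresses resection. The local-control curve is therefore an estimate for SBRT combined with discretionary surgery.

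Under the stated assumptions the upward shift at 12 months is about 6 to 13 points in the low scenario and about 1 to 3 points in the high one. These are bounds for surgery at month 3 with 2 or 4 of 18 resected, not predictions. The effect on the response rate is less certain, because it depends on reading complete response to include surgical removal.

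The consequence is limited. Local control is secondary, has no target or test, and the Cox comparison is declared non-inferential. The MTD decision is not touched.

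**What to change.** In Sections 8.1.4 and 9.3:

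1. For a resected patient, take response from the last scan before resection.
2. Report the local-control curve as now defined and, as a sensitivity analysis, a second curve censored at the date of resection. Label the first as including later surgery.
3. Give the number resected, by R0, R1 and R2.
4. Record the date of resection. Section 9.3 asks for margin status and the calendar in Section 7 has no row for surgery, so the documents do not show that the date is captured.

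The cost is one or two sentences, one extra curve and one data field, with no added patients or visits. No pre-operative scan is scheduled, so for some patients the last scan before resection may be the one at 3-5 weeks; the report should say so. Neither curve alone is definitive.
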